Subjects who meet study criteria for relapse at any point during the study will be withdrawn from the study and offered clinically-appropriate treatment as determined by the treating study physician, which may

include inpatient hospitalization, repeated administration of ketamine, electroconvulsive therapy (ECT), or other treatments determined by professional judgment. Subjects who demonstrate therapeutic benefit from experimental drug NRX-101 (DCS+ lurasidone) at study completion may be offered prescribed DCS by their treating psychiatrist.

The Schedule of Study Activities (Table 3) summarizes the frequency and timing of efficacy, PK, and safety measurements applicable to this study. With the exception of post-dose assessments, visit-specific subject-reported outcomes assessments should be conducted or completed before any tests, procedures, or other consultations for that clinic visit to prevent influencing subject perceptions. A recommended order of study procedures will be provided to sites as a separate document.

Actual dates and times of assessments will be recorded in the source documentation and electronic Case Report Form (eCRF).

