The investigators recognize that although DCS has been used as an anti-infective in millions of individuals without report of significant safety concerns, DCS has thus far been used in 21 subjects at the 1000mg dose in formal studies of psychiatric illness. Therefore, the study medical monitors will surveil for safety issues via frequent safety listings reviews.

The timing and incidence of adverse findings will be compiled following planned surveillance of all study subjects by study medical monitors. The number of such episodes will be evaluated using a Poisson regression model to compare study treatment groups controlling for C-SSRS 24 hours post infusion (1, 2), age (<25, 25-39, ≥40), and gender.

Vital signs will be obtained at every office visit. ECGs will be measured at the Screen Visits, and at Visits 1, 5, and 10. Digital ECGs will be obtained after the subject has been resting in a semi-recumbent position for at least 10 minutes. All digital ECGs will be documented by recording date, time, heart rate, QRS duration, PR interval, RR interval, QT, and QTcF intervals. Mean differences will be calculated using the Fridericia formula (Puddu et al., 1988). Vital signs and ECGs will also be evaluated within and between study treatment groups. If indicated, additional ECG assessments can be made at the discretion of the investigator. The investigator will judge the overall interpretation as normal or abnormal. If abnormal, it will be decided as to whether or not the abnormality is clinically significant or not clinically significant and the reason for the abnormality will be recorded on the eCRF. Abnormal values shall not be recorded as AEs unless deemed clinically significant.

At the Screen visit, and at Visits 1, 5, and 9, subjects will have their blood drawn for chemistry and CBC blood tests. At Screen, and at Visits 5 and 10, subjects will have a physical examination. If these tests or exams are abnormal per established site-specific normal ranges, it will be decided by the site investigator whether or not the abnormality is clinically significant or

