13.7.2 Other Safety Measures

The study is being conducted in a population who would likely have been admitted to a psychiatric hospital, if they did not have a positive response to ketamine. Moreover, it is expected that some subjects in the K/L and K/P treatment groups will have recurrence of their depression and, possibly suicidality. The timing and incidence of adverse findings will be compiled following planned surveillance of all study subjects by a designated safety monitor. The number of such episodes will be evaluated using a Poisson regression model to compare study treatment groups controlling for C-SSRS 24 hours post infusion (1, 2), age (<25, 25-39, ≥40), and gender.

Vital signs and ECGs will also be evaluated within and between study treatment groups. Mean differences in heart rate, QRS duration, PR interval, RR interval, QT, and QTcF. QTcF intervals will be calculated using the Fridericia formula (Puddu et al, 1988). The overall interpretation will be reported as normal or abnormal; if abnormal, then the percents clinically significant will be reported. Abnormal values shall not be recorded as AEs unless deemed clinically significant. McNemar paired comparison tests will be performed within study treatment groups for the abnormal percents while Fisher Exact tests will be performed between treatment groups.

While symptom improvement will be evaluated by assessing changes in the secondary outcome measures: C-SSRS, CHRT, BISS (MADRS), SIBQ and BPRS, safety measures in the PRISE, CADSS and BARS (including the global severity rating) will be evaluated within and between study treatment groups. The time frame is for both lifetime and the past six months for the Baseline/Screening scale and since the last visit for the Since Last Visit scale. Mean differences will be evaluated using a paired t-test with each study group and an unpaired t-test for K/N vs. K/L and K/P.

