13.8 Sample Size Calculations

13.8.1 Allocation

To encourage study participation, a 2:1:1 randomization will be used where at most half as many subjects will be assigned to the lurasidone and placebo arms as compared to the K/N study arm. The goal will be to have 62 subjects randomized to K/N and 31 subjects randomized to each of K/L and K/P for a total of 124 randomized subjects. The randomization takes place among Ketamine responders once confirmed by Medical Monitor.

13.8.2 Stage 1

The study goal is to achieve a total of 124 Ketamine responders for the Stage 2 evaluation. A total of 192 subjects are projected to be enrolled but this number may be reached sooner if the cumulative effect of the Ketamine response rate exceeding 70%, if the Stage 1 loss rate being less than 8% (15 subjects), or if the Stage 2 loss rate being less than 8% (9 subjects). Thus, there would be 177 subjects who complete Stage 1 before considering Ketamine response. The literature and prior experience suggests that 70% of those treated with ketamine will have an adequate reduction in depression and suicidality which equates to 124 Ketamine responders (177×0.7) who would be available for randomization. More subjects will need to be enrolled if the Ketamine response rate was lower than 70% or the randomization refusal rate was higher than 8%, considered to be part of Stage 2 losses.

13.8.3 Stage 2

Stage 2 will investigate the study hypotheses. The primary efficacy hypothesis is that K/N will delay the time to relapse relative to K/L and K/P. The goal will be to have 62 subjects randomized to K/N and 31 subjects randomized to K/L and K/P. These numbers are based on the Ketamine Responders. See **Error! Reference source not found.** for the total number of K/N and K/L subjects required to test the primary efficacy hypothesis. The sample size requirements are shown just for K/N and K/L. .

The study is powered based on the number of subjects randomized to K/N vs. K/L. In order to achieve 90% study power with two-sided 0.05 Type I error, a total of 56 K/N subjects, 28 K/L subjects, and 28 K/P subjects must be evaluated for time to relapse over the full 6 weeks. This is based on the assumption of a 30% relapse rate in the K/N treatment group and a 70% relapse rate in the K/L and K/P treatment groups. A larger gap in the relapse rate is expected based on the literature, so this is believed to be a conservative assumption. These calculations assume a loss of 8% during Stage 2.

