Table 12 Time to Relapse: K/N and K/L Groups Followed for 6 Weeks

	90% Power	Reaching Significance
Test significance level, α	0.05	0.05
1 or 2 sided test?	2	2
K/L relapse-free % p_1 at Week 6	30%	30%
K/N relapse-free % p_2 at Week 6	52%	70%
Hazard ratio, $h=\ln(p_1) / \ln(p_2)$	1.841	3.376
Power (%)	90	N/A
Total N	112	112
Total N of relapses required, R	48	62
Total N accounting for 8% Stage 2 losses	124	124
Total N accounting for 30% K non-responders	177	177
Total N accounting for 8% Stage 1 losses	192	192

The secondary efficacy hypotheses will also be evaluated using a hierarchical testing strategy where testing to support labeling claims continues as long as two-sided $p=0.05$ is reached. The first such hypothesis to be tested for the depression endpoints is whether K/N separates from K/L and K/P by 72 hours, with sustained difference between groups thereafter (see **Error! Reference source not found.**). There will be 90% power and two-sided 5% Type I error to detect a 0.754 effect size for the comparison of the K/N against the K/L and K/P treatment groups.

Table 13 Two Group T-test: Equal Effect Sizes

	90% Power	Reaching Significance
Test significance level, α	0.05	$p=0.05$
1 or 2 sided test?	2	2
Effect size, $\delta = \mu_1 - \mu_2 / \sigma$	0.754	0.456
Power (%)	90	N/A
Total N	112	112

Next, all-cause discontinuation (including discontinuation for continued suicidal ideation) will be tested. The hypothesis is that the percent discontinued prior to Week 6 will be lower in K/N than K/L and K/P using a lifetable approach (see **Error! Reference source not found.**).

Table 14 Two Group Log Rank Test: Time to All-cause Discontinuation

	90% Power	Reaching Significance
Test significance level, α	0.05	0.05
1 or 2 sided test?	2	2
K/L success rate p_1 at Week 6	0.225	0.225
K/N success rate p_2 at Week 6	0.6	0.43
Hazard ratio, $h = \ln(p_1) / \ln(p_2)$	3.89	1.77
Power (%)	90	N/A
Total N	112	112
Total # discontinued required, D	60	72

The next hypothesis to be tested is whether K/N will separate from K/L and K/P starting at Day 7, with sustained difference thereafter (see **Error! Reference source not found.**).

The next hypothesis to be tested is whether improvements within the K/N group observed at Week 2 will remain stable to end of study (see **Error! Reference source not found.**).

Table 15 One Group t-test: No Mean Change

	1	2	3	4
Test significance level, α	0.050	0.050	0.050	0.050
1 or 2 sided test?	2	2	2	2

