13.10.8 Safety Endpoints

Separate safety analyses will be performed for Stage 1, Stage 2, and combined across stages.

Adverse events will be classified by MedDRA. For each study treatment, safety data will be collected and analyzed while on Stage 1 or Stage 2 treatment or until treatment-emergent adverse events are resolved. The type, incidence, timing (onset, duration), relationship, and severity of AEs will be reported for treatment-emergent and SAEs. Reasons for withdrawal due to AEs will also be reported. Narratives will be written for every AE classified as serious or associated with attempted suicide or death.

Planned surveillance findings according to the designated safety monitor will also be analyzed. Adverse event timing will be displayed graphically. Overall incidence will be compared using a two-sided Fisher Exact test. The cumulative number of such episodes will be evaluated using a Poisson regression model to compare study treatment groups controlling for C-SSRS 24 hours post infusion (1, 2), age (<25, 25-39, >40), and gender.

Vital signs and ECGs (means and mean changes from Stage 1 and Stage 2 baselines) will also be evaluated within treatment groups using paired t-tests and between study treatment groups using unpaired t-tests. Percents with abnormal vital signs, heart rate, QRS duration, PR interval, RR interval, QT, and QTcF will be reported. McNemar paired comparison tests will be performed within study treatment groups for the abnormal discordant percents while two-sided Fisher Exact tests will be performed to compare incidences between treatment groups.

Blood draws for chemistries and hematologies will be evaluated within and between study treatment groups. Abnormality rates will be presented relative to established site-specific normal ranges and whether or not the abnormality is clinically significant. McNemar paired comparison tests will be performed within study treatment groups for the abnormal percents while two-sided Fisher Exact tests will be performed to compare incidences between treatment groups.

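### The Poisson comparison of adverse episodes names no exposure term, although follow-up is expected to be shorter in the control arms; the exposure handling, the episode and the at-risk window all need defining

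*Combined protocol and SAP*

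**What the plan says.** The same count model appears in three places.

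- Section 13.7.2: "The number of such episodes will be evaluated using a Poisson regression model to compare study treatment groups controlling for C-SSRS 24 hours post infusion", with age group and gender completing the list.
- Section 8.2.5.2.3: "The number of such episodes will be evaluated using a Poisson regression model to compare study treatment groups", with the same three covariates.
- Section 13.10.8: "The cumulative number of such episodes will be evaluated using a Poisson regression model to compare study treatment groups", again with the same covariates.

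None of these, and no other section, mentions an offset, person-time or an exposure-adjusted rate.

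Three other statements determine how long each subject is observed.

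- Section 8.1: "Subjects who meet study criteria for relapse at any point during the study will be withdrawn from the study".
- Section 13.10.8: "safety data will be collected and analyzed while on Stage 1 or Stage 2 treatment or until treatment-emergent adverse events are resolved".
- Section 13.8.3 assumes a "30% relapse rate in the K/N treatment group and a 70% relapse rate in the K/L and K/P treatment groups".

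The randomization target in section 13.8.1 is "62 subjects randomized to K/N and 31 subjects randomized to each of K/L and K/P".

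**The concern.** A Poisson model without an exposure term estimates episodes per subject. That is a fair comparison only when the arms are observed for similar lengths of time. Here the design expects more than twice as many control subjects as K/N subjects to relapse and leave. If NRX-101 works as hoped, its recipients stay longer and have more time in which to record an adverse episode.

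The comparison could then show an apparent excess on K/N that reflects only follow-up time, or could mask a real excess rate in controls. Section 8.2.5.2.3 gives the reason to care: DCS at 1000 mg has been used in only 21 subjects in formal psychiatric studies, so readers will look closely at any between-arm safety contrast.

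**Working it through.** **Inputs.** Week 6 relapse-free proportions S are 0.70 (K/N) and 0.30 (controls), from section 13.8.3. Table 12, in the row labelled "K/L relapse-free % p_1 at Week 6" and the row below it, also gives 0.30 against 0.52. Treatment lasts 42 days. Group sizes are 62 and 31 for each pairwise comparison. Episode rates and timing are not in the documents and are assumed below.

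**1. The plan's own figure.** Table 12 uses hazard ratio = ln(p1)/ln(p2).
- ln(0.30)/ln(0.70) = 1.2040/0.3567 = 3.376, as stated.
- ln(0.30)/ln(0.52) = 1.2040/0.6539 = 1.841, as stated.

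That formula corresponds to exponential relapse, which I use as the base case.

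**2. Mean observed time**, if observation stops at relapse or Day 42: 42 × (1 − S)/(−ln S).
- K/N: 42 × 0.30/0.3567 = 35.3 days.
- Controls: 42 × 0.70/1.2040 = 24.4 days.
- Ratio: 1.45.

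With a common constant episode rate, expected counts per subject are proportional to these times. The model as listed then has an expected ratio of 1.45 whatever the rate. The 2:1:1 allocation plays no part, because the comparison is per subject.

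**3. Sensitivity of that ratio** (equal episode rates, relapse not counted):

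| Change from the base case | Calculation | Ratio |
|---|---|---|
| 52% vs 30% relapse-free (Table 12) | 30.8/24.4 | 1.26 |
| Relapse linear in time | 35.7/27.3 | 1.31 |
| 30 further days of capture for everyone | 65.3/54.4 | 1.20 |
| Completers observed to Day 70, relapsers stop at relapse | (35.3 + 28 × 0.70)/(24.4 + 28 × 0.30) = 54.9/32.8 | 1.67 |
| Discontinuation as in Table 14 (0.60 vs 0.225) | 32.9/21.8 | 1.51 |
| Episode rate halving every 3, 7 or 14 days | see below | 1.08, 1.18, 1.28 |

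For the last row, the expected count per subject is proportional to (1 − exp(−42(λ + k)))/(λ + k), with λ = −ln(S)/42 and k = ln 2/half-life. More extreme choices go further: 1.05 with 52% relapse-free and a 3-day half-life, and 1.80 if every relapse fell on Day 7.

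**4. Chance of a false signal against K/N.** This comes from 20,000 simulated trials per setting, 62 vs 31, with a constant equal episode rate, exponential relapse at 30% vs 70%, and a two-sided 0.05 Wald test (nominal 2.5% in this direction).

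| Assumed episodes per subject per 42 days | No offset | log person-time offset |
|---|---|---|
| 0.5 | 14% | 1.3% |
| 1 | 27% | 2.1% |
| 2 | 50% | 2.3% |
| 3 | 63% | 2.2% |

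With 52% vs 30% relapse-free, the no-offset figures are 7%, 13%, 25% and 34%.

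**5. If each relapse is itself an episode.** Let r be the rate of other episodes per 42 days. Since 35.3/42 = 0.841 and 24.4/42 = 0.581, the raw ratio is (0.841r + 0.30)/(0.581r + 0.70).
- r = 0.5 gives 0.73 and r = 1 gives 0.89.
- r = 2 gives 1.06 and r = 3 gives 1.16.
- The ratio crosses 1 at r = 0.40/(0.841 − 0.581) = 1.54.

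**6. Would one overall offset be enough?** Only if the episode rate is constant. With the equal front-loaded rates of step 3, dividing by 1.447 gives 1.08/1.447 = 0.75, 1.18/1.447 = 0.82 and 1.28/1.447 = 0.88, so K/N would look falsely safer. Splitting follow-up by week, with person-time as offset and a period term, returns 0.98 to 1.00 for the same three cases.

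**The case against.** Five points can fairly be made against the concern.

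- **An offset is not excluded.** The plan lists covariates to control for, and an offset is not a covariate. Sections 6.4 and 13 also promise full pre-specification in a SAP. This stands: the exposure term is unspecified, not rejected. But the model is spelled out three times without it, and leaving it open allows the choice to be made after the data are seen.
- **The episodes may include relapse.** A reader might infer that K/N is bound to look less safe at identical rates. The documents do not support that, because the episodes are never defined. In section 13.7.2 the model follows a remark that controls are expected to have recurrent depression and possibly suicidality. Section 12.1 makes clinically significant worsening of suicidal ideation an AE, while sections 12.3 and 12.5 keep worsening bipolar depression out of AEs. If relapse-type events count, the rates are not identical and the direction can reverse (step 5). This stands.
- **Capture does not stop dead at relapse.** SAEs are collected to 30 days after the last dose (section 12.6), there is an early termination visit (8.1.7), and discontinued subjects are followed where possible (9.5). These narrow the gap but do not equalise observation of all episodes.
- **A plain offset could mislead the other way.** Dose is titrated over the first five days (Table 6), and section 8.1 has discharged subjects contacted twice daily for a week and then at least weekly, so early clustering of recorded events is plausible. This stands and changes the remedy.
- **Little depends on this model.** The main AE comparisons are Fisher tests (sections 8.2.5.2.1 and 13.7.1), and the model lies outside the hierarchy in section 13.9. This stands for severity, although the Fisher tests compare incidence over the same unequal follow-up.

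**Conclusion.** The concern holds in a limited form. As listed, the Poisson model compares counts per subject over follow-up that the design expects to differ by arm. For non-relapse episodes at equal rates, and with fewer relapses on K/N, the ratio exceeds 1 in every scenario examined. The figure of 1.45 is one scenario, resting on 30% vs 70% relapse, exponential timing, a constant episode rate and no capture after relapse. About 1.08 to 1.67 is a reasonable span. The false-signal percentages rest further on assumed episode rates.

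The documents do not support a claim that the analysis must disfavour NRX-101. With equal relapse across arms there is no such bias, and if relapse-type events are counted the sign depends on the background rate. Because the analysis is supportive and outside the testing hierarchy, the severity is minor to moderate.

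**What to change.** In sections 8.2.5.2.3, 13.7.2 and 13.10.8:

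1. Model episodes by study week with log person-time at risk as offset and a period term, keeping the listed covariates. The minimum is a split between the titration week and later; weekly periods protect better against early clustering.
2. State whether relapse-defining events count as episodes.
3. Use one at-risk window. Section 6.4 runs the Stage 2 Safety Population's data through Day 70, section 13.3 sets no end, and section 13.10.8 stops at the end of treatment or at AE resolution. These must be reconciled.
4. Show exposure-adjusted incidence beside the Fisher tests.

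The cost is a short SAP revision, somewhat more programming and slightly wider intervals. No new data are needed: assessment dates (section 8.1), dosing dates and times (9.2) and time to discontinuation (13.10.7) are already captured.

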6.2 Methods

[figure not shown]
In Stage 1 eligible subjects will initially receive an infusion of open-label ketamine 0.5mg/Kg. Those who do not respond to ketamine infusion as measured by a $\geq 25\%$ improvement in the MADRS subset on the BISS and a reduction in C-SSRS suicidal ideation to ≤ 3 at 24 hours post infusion will be withdrawn from the study and treated according to standard of care for subjects with suicidal ideation or behaviors.

Subjects who respond successfully to ketamine infusion, as defined above ($\geq 25\%$ improvement in the MADRS subset of the BISS and C-SSRS ≤ 3) at 24 hours post infusion will proceed to Stage 2 and be randomized to either experimental drug NRX-101 (DCS + lurasidone), lurasidone alone, or placebo. Efficacy data will be collected for the subjects responding to ketamine through 6 weeks or until earlier rescue.

Subjects may be terminated from the study and rescued with alternative therapy at any time if, in the opinion of the investigator, subjects have a significant safety risk for clinical deterioration or suicide.

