13.10.3 Conventions

Means, mean changes, standard deviations, and ranges will be presented separately for Stage 1 and then for each Stage 2 treatment group over time. These endpoints will be evaluated within the three study treatment groups for the change from Stage 1 and Stage 2 baselines using a paired t-test and between study treatment groups using an unpaired t-test at each time; these p-values will be presented as descriptive statistics.

For continuous variables, the mean, standard deviation, minimum, median and maximum will be presented, together with the total number of observations and the number of missing and non-missing values. Unless otherwise specified minimum and maximum values will be reported to the same number of decimal places as the recorded measurements, mean and median are reported to one more decimal place and standard deviation one additional decimal place more than the mean.

For ordinal and categorical variables, absolute and relative frequencies will be reported. Relative frequencies will be based on all observations and reported as percentages to one decimal place. Unless otherwise specified percentages will be based on the number of subjects with data and will not be calculated for missing categories.

Adverse events, medical histories and concomitant medications will be reported on a subject and an event basis. The percentages will be calculated using the number of subjects in the population Analysis Set as the denominator.

All hypotheses will be tested at 5% (final analysis) level of significance using a two-sided test unless otherwise specified.

P-values will be rounded to four decimal places. If a p-value is less than 0.0001 it will be reported as “<0.0001.” If a p-value is greater than 0.9999 it will be reported as “>0.9999”.

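### The Poisson comparison of surveillance episodes makes no allowance for variance unequal to the mean, and because the episodes are undefined the test could be too liberal or too conservative

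*Combined protocol and SAP*

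**What the plan says.** Section 13.7.2 describes the data: "The timing and incidence of adverse findings will be compiled following planned surveillance of all study subjects by a designated safety monitor". It then gives the analysis: "The number of such episodes will be evaluated using a Poisson regression model to compare study treatment groups", controlling for C-SSRS at 24 hours after infusion, age band and gender. Section 8.2.5.2.3 specifies the same model. Section 13.10.8 applies it to a cumulative count: "The cumulative number of such episodes will be evaluated using a Poisson regression model to compare study treatment groups". It also compares overall incidence with a two-sided Fisher exact test.

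None of these sections mentions a scale parameter, a robust variance or another count model. Section 13.10.4, by contrast, adds an empirical sandwich variance to the MMRM to guard against a wrong covariance structure. The level is set in Section 13.10.3: "All hypotheses will be tested at 5% (final analysis) level of significance using a two-sided test unless otherwise specified".

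Two other sections affect what the counts can look like. Section 8.1 withdraws subjects who meet the relapse criteria. Section 12.1 says that subjects with clinically significant emergence or worsening of suicidal ideation or behavior should be withdrawn.

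**The concern.** An ordinary Poisson regression takes its standard errors from the assumption that, given the covariates, each subject's count has variance equal to its mean. That is an assumption of the model and not part of the null hypothesis of equal rates. If it fails, the rates can be equal and the p-value still wrong.

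It can fail in two directions. Some subjects may be more prone to adverse findings than others with the same C-SSRS, age band and gender, for instance because background drugs (Section 9.2), doses (Table 6) and site of care (Section 8.1) differ. Repeated findings then concentrate in those subjects, the variance exceeds the mean, and the test rejects too often. If instead a subject can contribute at most one episode, the variance is below the mean and the test rejects too rarely.

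At stake are the p-values and confidence intervals for K/N against K/L and K/P on these episodes. In the first case a false safety signal or a false safety advantage becomes more likely. In the second a real difference may go unnoticed.

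**Working it through.** **Inputs**

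- Level: 0.05 two-sided (Section 13.10.3), critical value 1.96.
- Arms: "62 subjects randomized to K/N and 31 subjects randomized to each of K/L and K/P for a total of 124 randomized subjects" (Section 13.8.1).
- Model terms: arm, 24-hour C-SSRS (two levels), age band (three) and gender (Section 13.7.2).
- φ, the ratio of variance to mean of a subject's count given the covariates: not in the documents. Assumed to be 1.5 to 3 for repeated findings.
- Mean episodes per subject: not in the documents. The simulations tabulated below for repeated findings used 0.5 and 1.

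**Step 1: reproduce the nominal level.** If the variance is φ times the mean, the true standard error is √φ times the model's, so

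size = 2 × [1 − Φ(1.96/√φ)].

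At φ = 1 this is 0.050, the stated level. Simulated Poisson counts at 62/31/31 with the covariates gave 4.2–5.7%.

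**Step 2: repeated findings that cluster (φ above 1).** Simulated counts were gamma-mixed Poisson with equal true rates, 1,500 trials per setting.

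| Assumed φ | 1.96/√φ | Size by formula | Simulated |
|---|---|---|---|
| 1.5 | 1.600 | 0.110 | 0.099–0.115 |
| 2 | 1.386 | 0.166 | 0.149–0.161 |
| 3 | 1.132 | 0.258 | 0.261–0.275 |

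Further simulations of the same design gave about 8–11% at 1.5, 13–19% at 2 and 22–26% at 3. The low end comes from sparse counts: a mean of 0.3 per subject gave 8.8% at φ = 1.5. The highest cells in the table, 11.5% and 27.5%, agree with the formula within simulation error. The standard errors are √(0.110 × 0.890/1500) = 0.8 and √(0.258 × 0.742/1500) = 1.1 percentage points.

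**Step 3: at most one episode per subject (φ below 1).** For a 0/1 count with probability p, variance/mean = p(1 − p)/p = 1 − p. The values 0.3 and 0.7 are the relapse rates assumed in Section 13.8.3, used here as a common probability in all arms so that the null holds.

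| p | φ = 1 − p | 1.96/√φ | Size by formula | Simulated |
|---|---|---|---|---|
| 0.3 | 0.7 | 2.343 | 0.019 | 0.011–0.015 |
| 0.5 | 0.5 | 2.772 | 0.006 | 0.003–0.005 |
| 0.7 | 0.3 | 3.578 | 0.0003 | 0.000–0.002 |

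**Step 4: does a scaled standard error repair both?** Estimate φ as the Pearson chi-square divided by its residual degrees of freedom. The model has 7 parameters (intercept 1, arm 2, C-SSRS 1, age 2, gender 1), so these are 124 − 7 = 117. Multiply each standard error by the square root of the estimate.

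| Data | Pearson-scaled size |
|---|---|
| True Poisson | 4.3–5.6% |
| Overdispersed, φ from 1.125 to 7 | 3.6–6.0% |
| 0/1 counts | 3.4–4.8% |

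An unadjusted sandwich variance gave 5.1–7.9% on the overdispersed data, somewhat liberal at this sample size. A small-sample-adjusted sandwich was not simulated.

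**The case against.** The strongest objection is that the documents establish neither clustering nor its amount. A reader might infer that the test rejects two to six times too often. The formula gives that range only for φ between 1.42 and 3.58. At φ = 1.1 the factor is 1.2, and at φ = 6 it is 8.5. No mean, variance or dispersion is stated from which to choose, so that inference is not supported.

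Even the direction is open. In Section 13.7.2 the phrase *such episodes* comes shortly after a remark that depression, and possibly suicidality, will recur in some subjects. Subjects with those events are to be withdrawn (Sections 8.1 and 12.1), which points to counts near 0 or 1 and a conservative test. Against this, Section 13.10.8 analyses a cumulative number separately from overall incidence, which adds information only if a subject can have more than one episode. Both readings are reasonable, and the text does not choose between them. That objection stands, but it does not rescue the model-based variance, which is unreliable under both readings.

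It can also be said that naming a Poisson regression does not rule out a scale option, and that Sections 6.4 and 13 promise pre-specification of all analyses in a SAP. That is fair, but the choice still has to be written down, and three sections describe this analysis without it.

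Finally, the consequence is limited. Section 13.9 places only the primary and secondary efficacy hypotheses in the testing hierarchy, and the Fisher test of incidence is not affected by repeated episodes. This stands and lowers the severity. The Fisher test does not, however, protect the rate comparison or its interval.

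**Conclusion.** The point holds in conditional form. The plan compares episode counts with a Poisson regression that makes no stated allowance for variance different from the mean, and it does not define the episodes.

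- If repeated findings cluster, with an assumed ratio of 1.5 to 3, the nominal 5% test has a size of about 8–11% at the lower ratio and 22–26% at the upper.
- If an episode is a relapse or suicidality event that ends participation, the size is about 0–2% and a real safety difference could be missed.

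The first result rests on an assumed dispersion and on mean counts that the documents do not give. The second rests on reading the withdrawal rules as capping the count near one. Because the comparison lies outside the Type I error hierarchy and has an incidence test alongside, the severity is low.

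**What to change.** In Sections 8.2.5.2.3, 13.7.2 and 13.10.8:

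1. State which surveillance findings count as episodes and whether a subject can contribute more than one.
2. Keep the Poisson regression and its covariates, but base tests and intervals on a Pearson-scaled standard error with the scale free to fall above or below 1. A sandwich variance with a small-sample adjustment is an alternative.
3. Report the rate ratio for K/N against K/L and against K/P, each with its confidence interval.

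The negative binomial model should not be the default. Its variance cannot fall below the mean, so it does not repair the 0/1 case. In one check on such counts its fits failed to converge in 62–98% of runs.

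The cost is one model option and a definition. With truly Poisson counts almost nothing is lost. With overdispersed counts the intervals widen by √φ, that is by a factor of √1.5 = 1.22 or √3 = 1.73 at the two assumed ratios, which is the width the data warrant.
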